Efficacy of an Attention Guidance VR Intervention for Social Anxiety Disorder

Statistical Analysis Plan

Date: 06/20/2021

Identifiers: NCT03683823 Unique Protocol ID: 2018-04-0011

Data Analysis Plan

The primary aims of this study were to 1) examine whether an attention guidance augmentation enhanced VRET compared to VRET alone and 2) test whether changes in gaze behavior following the intervention mediated the effects VRET. To test our primary hypotheses regarding the influence of the intervention on fear of public speaking (PRPSA), we conducted Bayesian multilevel models using the *brms* package version 2.15 (Bürkner, 2018). For aim 1 we examined the interaction between assessment and group predicting the outcome post-treatment and at 1-week-followup. For aim 2, we examined the indirect (i.e., mediating) effect of proportion of fixations to uninterested (socially threatening audience members) at the post-treatment assessment, on the relationship between intervention group and the post-treatment assessment of PRPSA at the 1-week-followup (see Figure 3). To facilitate interpretation of the mediation analysis, we partially standardized the model coefficients after completing the analyses using unstandardized variables following recommendations in the literature regarding indirect effect sizes when X is dichotomous (Hayes & Rockwood, 2017; Preacher & Kelley, 2011). In all models, we included average proportion of fixations to audience members during intervention sessions as a covariate to control for variation in treatment adherence. We completed the same analyses to evaluate our secondary outcome of general social anxiety symptoms measured with the LSAS. As integrity checks on the efficacy of the attention augmentation condition we tested whether there were group differences for average number of fixations on audience members during the intervention trials, as well as whether there were differences in proportion of fixations to uninterested audience members post-intervention and at 1-week follow-up.

We computed Bayes Factors (BFs) using the Savage-Dickey Density ratio (Wagenmakers et al., 2010) for all models where we set priors using the *hypothesis* function in *brms*. The Savage-Dickey Density ratio was calculated in the current context by dividing the posterior density by the prior density at zero (a null effect). Given that priors exert a large influence on the posterior estimates with small samples sizes, we used BFs to provide a sense of the influence of the priors on the study data rather than using them to provide a measure of confidence in the posterior estimates themselves as they are sometimes used (in *brms* if the *hypothesis* function is directional, it provides the latter estimate rather than the Savage-Dickey Density ratio). A BF equal to one means there is equal support for the null and alternative hypotheses while smaller BFs reflect greater support for the null and larger BFs reflect greater support for the alternative, with commonly accepted guidelines for the magnitude of the support (e.g., 1-3 is anecdotal evidence in favor of the alternative; 1/3-1 is anecdotal evidence in favor of the null).

For each result we report the beta estimates, 95% highest posterior density interval (HDI), and BFs of the model estimated with our original prior. We also provide the range of BFs as well as the sensitivity of the beta estimates based on our sensitivity analyses (see below).

Prior Estimates. We set informative priors based on expected effects that were based on a literature review of brief exposure-based intervention for social anxiety, as well as based on expert review. On a theoretical level, use of priors aligns with the idea that all available data should be used to draw inferences – including data from previous findings (Kruschke & Liddell, 2018). On a more practical level, there is substantial evidence to support the use of informative priors to address the ‘winner’s curse’ – which is where significant effects in an initial study are not subsequently replicated (Altoè et al., 2020). Moreover, Lemoine (2019)

conducted simulation analyses showing that weakly informative priors can regularize results in small samples ($n < 50$), providing a more conservative estimate.

We largely followed the WAMBS (When to worry and how to Avoid the Misuse of Bayesian Statistics) checklist (Depaoli & van de Schoot, 2017). This checklist provides a step-by-step approach to ensuring that a model estimation procedure is acceptable and that the influence of the priors is well delineated. We tested the sensitivity of the priors by using less informative (smaller effects) parameter estimates as well as uninformative default (flat) priors centered on zero to determine the influence of different priors on the posterior estimates.

Priors for the effect of the intervention on fear of public speaking (PRPSA) were primarily based on a relatively recent study which also used a two-session public speaking exposure model (testing affect labeling as a potential mechanism; Niles et al., 2015). In terms of the efficacy of the augmentation for which there is no previous research, we used a prior that reflected a moderate effect ($\Delta 10$ on PRPSA score). It was impossible to predict whether there would be a greater gain at post-treatment followed by a ‘rebound’ (i.e., regression towards the mean) or whether the gains would continue and we tested the sensitivity of our priors by varying the magnitude of the effects as well as their direction (to a certain degree). We also tested a model with uninformative priors, centered on zero. Similarly, for the LSAS we used previous research to determine the priors. One challenge was that most studies addressing fear of public speaking did not have a clinical sample of socially anxious individuals – we predicted greater severity of social anxiety symptoms in the current study – and so drew from other studies as well (Lazarov et al., 2018). We primarily based our estimates of the efficacy of the intervention using a recently published single-session feasibility VRET study (Lindner et al., 2021). The estimate of the effect of the intervention provided a good starting place to inform our priors – based on the

likelihood that 2 sessions would be more potent, we also used estimates from other longer intervention studies.

Priors on the effects of the intervention on proportions of fixations to audience members were not based on previously collected data because there is no literature that clearly delineates expected changes in gaze during public speaking challenges. We chose priors that reflected modest but meaningful effects, indicating changes in gaze behavior substantial enough to have potential implications for treatment outcomes as a causal mechanism. As with the other analyses, we tested several priors reflecting smaller effects as well as an uninformative prior centered on zero.

Power analysis. We did not conduct a power analysis that reflected the sample size for the current pilot study. We had initially conducted a power analysis through a simulation study prior to COVID-19, which indicated a sample size of 60 would be sufficient to detect a meaningful effect for both aims 1 and 2. However, due to COVID-19 enrollment ended before we could meet our recruitment goals. Given that research was necessarily stopped, we decided to rely on the strengths of the Bayesian approach highlighted above to investigate whether it would be worthwhile to conduct a more extensive RCT with a larger sample.

Data and syntax are available at <https://osf.io/un92m/>.

References

Bürkner, P. C. (2018). Advanced Bayesian multilevel modeling with the R package brms. *R Journal*. <https://doi.org/10.32614/rj-2018-017>

Depaoli, S., & van de Schoot, R. (2017). Improving transparency and replication in Bayesian statistics: The WAMBS-checklist. *Psychological Methods*. <https://doi.org/10.1037/met0000065>

Hayes, A. F., & Rockwood, N. J. (2017). Regression-based statistical mediation and moderation analysis in clinical research: Observations, recommendations, and implementation. *Behaviour Research and Therapy*. <https://doi.org/10.1016/j.brat.2016.11.001>

Kruschke, J. K., & Liddell, T. M. (2018). Bayesian data analysis for newcomers. *Psychonomic Bulletin and Review*. <https://doi.org/10.3758/s13423-017-1272-1>

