Screen capture data: Screen capture data (of the fixation dot in the virtual environment) will be collected with the GeForce application. This will allow us to check that the eye movements made during the speech are being analyzed correctly by the algorithm that uses the data recorded during eye-tracking. Screen capture data also includes video of the eyes of the participants, which is used to check tracking data when the eyes are closed (e.g. during blinks).

Participants

a. Target Population

Participants will include men and women who are community volunteers and undergraduate students at the University of Texas at Austin ($N = 80$). The expected ethnicity of the sample based on previous studies in this laboratory is Caucasian (74%), Mexican-American (13%), African-American (7%), Asian-American (5%), and Indian-American (1%). During the consent process, all participants will be clearly informed that they can withdraw from the study at any point in time without consequences (e.g., Psychology 301 participants will still receive full credit for their visit). Participants will

Research Proposal

complete the study in 3 sessions. We will recruit up to 200 participants to ensure that we have at least 80 participants complete the study.

b. Inclusion/Exclusion

Some of the measures (PRPSA, SCID-5) used in this study have not been validated in a language other than English; therefore, participants not fluent in English will be excluded.

Inclusion Criteria:

- (1) Age 18-65 (Online pre-screen & Baseline assessment – self-reported)
- (2) Fluent in English (Online pre-screen & Baseline assessment – self-reported)
- (3) Personal Report of Public Speaking Anxiety > 98 (Online pre-screen & Baseline assessment – self-reported)
- (4) Leibowitz Social Anxiety Scale > 30 (Online pre-screen & Baseline assessment – self-reported)
- (5) Peak fear ≥ 50 or average fear ≥ 50 on the behavioral approach task during the baseline assessment (Baseline Assessment – BAT)
- (6) Meets DSM-5 Criteria for Social Anxiety Disorder (Baseline assessment – SCID-5).

Exclusion Criteria:

- (1) Currently receiving CBT for Social Anxiety Disorder (Online pre-screen self-reported)
- (2) Significant visual impairment precluding the use of virtual reality equipment (Online pre-screen self-reported)
- (3) Unstable dose of psychotropic medications within 3 weeks prior to baseline assessment (Online pre-screen self-reported)

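### Aim 1 rests on a group-by-assessment interaction with no stated baseline adjustment or equal-baseline constraint, which probably costs precision, and the intervention-session gaze covariate must come out if baseline adjustment goes in

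*SAP*

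**What the plan says.** The SAP, under Data Analysis Plan, states that for the public-speaking outcome "we conducted Bayesian multilevel models using the" brms package, and that "For aim 1 we examined the interaction between assessment and group predicting the outcome post-treatment and at 1-week-followup". LSAS is handled alike: "We completed the same analyses to evaluate our secondary outcome of general social anxiety symptoms measured with the LSAS". One covariate is named: "In all models, we included average proportion of fixations to audience members during intervention sessions as a covariate". The SAP does not write the model formula, list the levels of assessment, describe the random effects, or say whether the group main effect is free, omitted or given a prior.

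The protocol's inclusion criteria require "Personal Report of Public Speaking Anxiety > 98" and "Leibowitz Social Anxiety Scale > 30", both checked at pre-screen and again at the baseline assessment. Protocol section 4 places randomisation after that assessment. Both baseline scores therefore exist for everyone randomised, and any difference between arms at baseline is due to chance.

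On size, the SAP's Power analysis paragraph reports that "due to COVID-19 enrollment ended before we could meet our recruitment goals". The number enrolled is not given.

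**The concern.** The sentence on aim 1 has two possible readings, and neither makes good use of baseline.

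- **Three levels (baseline, post-treatment, 1 week).** With the usual expansion of group by assessment, the interaction at each visit is the between-arm difference in change from baseline. This fixes the slope of follow-up on baseline at 1 and does not use the fact that randomisation makes the expected baseline means equal.
- **Two levels (post-treatment, 1 week).** The interaction asks only whether the group effect differs between the two visits. If the benefit is D at both, it equals D − D = 0. Baseline is not used at all.

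On either reading, the quantity of interest is the baseline-adjusted group difference at each visit. Enrolment stopped short, and the result is meant to inform whether a larger trial is worthwhile. The SAP also accepts that priors weigh heavily in small samples, and a less precise likelihood gives them still more weight.

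**Working it through.** **Inputs.** From the documents: two arms; PRPSA and LSAS measured before randomisation; a prior for the augmentation of 10 PRPSA points (SAP, Prior Estimates). Not in the documents, so assumed: equal allocation, complete data, baseline-to-follow-up correlation ρ of 0.4 to 0.7, follow-up PRPSA SD of 15 or 20, and 15 or 30 per arm.

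**The plan's own figure.** The SAP's sample size of 60 cannot be reproduced, because its effect, SD, correlation, error rate and power are not given. If the effect were 10 points in a post-only comparison at two-sided 5% and 80% power, 60 would fit an SD of about 13.6 to 13.8. An SD of 15 would need 72 participants and an SD of 20 would need 126. The figure therefore does not settle SD or ρ.

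**Step 1: what the interaction estimates.** In 300 simulated trials at each of ρ = 0.5 and 0.7 (60 participants, three assessments, random intercept, gaze covariate as a participant-level main effect), the fitted interaction equalled the difference in mean change with a maximum discrepancy of 0. The gaze covariate therefore does not stand in for baseline adjustment.

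**Step 2: variance ratio.** Let k = follow-up SD / baseline SD. In units of the baseline variance, the per-person variance is 1 + k² − 2ρk for the change contrast and k²(1 − ρ²) for the adjusted one. The ratio is

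k²(1 − ρ²) / (1 + k² − 2ρk), which is (1 + ρ)/2 when k = 1.

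A baseline SD of 0.8 of the follow-up SD gives k = 1/0.8 = 1.25. Estimating the slope costs a factor of about (N − 3)/(N − 4), which is 27/26 at 15 per arm.

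| ρ | k = 1 | k = 1.25 | k = 1.25, 15 per arm | slope ρk at k = 1.25 |
|---|---|---|---|---|
| 0.4 | 0.70 | 0.84 | 0.87 | 0.50 |
| 0.5 | 0.75 | 0.89 | 0.93 | 0.625 |
| 0.6 | 0.80 | 0.94 | 0.98 | 0.75 |
| 0.7 | 0.85 | 0.98 | 1.02 | 0.875 |

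Simulation at 15 per arm agrees with the fourth column to within about 0.01.

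**Step 3: on the PRPSA scale** (follow-up SD 20, ρ = 0.5, 15 per arm, large-sample formulas). At equal SDs, the SE is 20 × √(2 × 1.00/15) = 7.3 for the interaction and 20 × √(2 × 0.75/15) = 6.3 adjusted. With baseline SD 16, the change variance is 256 + 400 − 320 = 336, so the SEs are √(2 × 336/15) = 6.7 and 6.3.

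**Step 4: chance imbalance.** The interaction differs from the adjusted estimate by (1 − slope) × the baseline difference. A one-SE imbalance at 15 per arm is 20 × √(2/15) = 7.3 points at equal SDs, giving a shift of 0.5 × 7.3 = 3.7 points. With baseline SD 16 it is 5.8 points, giving 0.375 × 5.8 = 2.2. The SAP's moderate effect is 10.

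**Step 5: effect of a prior.** With 60 participants, SD 15 and ρ = 0.5, the sampling variances are 15.0 and 11.25 (ratio 0.75). A prior SD of 5 (assumed) gives posterior variances of 1/(1/15 + 1/25) = 9.4 and 1/(1/11.25 + 1/25) = 7.8, a ratio of 0.83.

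**Step 6: keeping the gaze covariate in an adjusted model.** Suppose the arms differ by 1.5 within-arm SDs in intervention-session gaze. The squared correlation of gaze with group is 0.75²/(1 + 0.75²) = 0.36, so the variance of the group difference is multiplied by 1/(1 − 0.36) = 1.56 when gaze is otherwise unrelated to outcome. Against the interaction, 0.70 × 1.56 = 1.09 and 0.98 × 1.56 = 1.53. Simulation in small arms gave 1.1 to 1.8. If a 10-point benefit acted wholly through gaze, the interaction would still recover 10, but the gaze-adjusted difference would be about 0.

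**The case against.** The strongest reply is that the SAP never says the baseline difference was left free. It gives no formula, and the group term may have been omitted or given a prior, which would act as a full or partial equal-baseline constraint. The syntax is said to be posted, but it is not part of the documents reviewed. This stands: the usual reading is an inference. It does not remove the request, because the plan should state which model it used, and the two-level reading is no better.

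Second, the identity with the change score holds for flat priors and complete data, while the SAP's main analysis uses informative priors. This also stands, and it narrows the gain (step 5).

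Third, a reader might infer that adjustment is worth 18% to 43% more participants at no cost (1/0.85 = 1.18; 1/0.70 = 1.43). The documents do not support this. Those figures need equal SDs, whereas the entry thresholds truncate the baseline scores. With k = 1.25 and 15 per arm, the gain runs from modest to none.

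Fourth, a reader might infer that the aim 1 analysis is biased or invalid. It is not: averaged over randomisation the interaction is unbiased, and it is a standard longitudinal contrast.

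Fifth, under the SAP's rule that gaze enters every model, adding baseline alone could leave aim 1 worse off. This stands and changes the remedy.

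**Conclusion.** The concern holds as a matter of precision and of conditional imbalance, not validity. The SAP names neither baseline adjustment nor an equal-baseline constraint, although both scores are available for every randomised participant. On the usual three-level reading, the interaction has the larger variance in large samples whenever the slope differs from 1, and it over-corrects chance imbalance when the slope is below 1. For ρ of 0.4 to 0.7, the adjusted-to-interaction variance ratio is 0.70 to 0.85 at equal SDs and 0.84 to 0.98 at a baseline SD of 0.8 of the follow-up SD (about 0.87 to 1.02 at 15 per arm). Informative priors bring it closer to 1. These ranges rest on assumed SDs, correlations and arm sizes, so the documents cannot show where the trial falls. On the two-level reading the ratios do not apply; there the problem is that baseline is ignored and a constant benefit is invisible to the interaction.

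**What to change.** State the aim 1 formula, the levels of assessment, and the treatment of the group term, including any prior on it. Then fit

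`outcome at post-treatment and 1 week ~ group × assessment + baseline score × assessment + (1 | participant)`

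for PRPSA, and likewise for LSAS with its own baseline. Report the adjusted group difference at post-treatment and at 1 week as the aim 1 results. Put the augmentation prior on those two differences; coding the model so that each is a coefficient makes this direct.

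Say explicitly that the intervention-session gaze covariate is left out of this model. It is measured after randomisation and is what the experimental arm sets out to change, so keeping it would inflate the variance and could adjust the effect away. This is a second change to the SAP, because the present text puts that covariate in every model.

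Keeping three assessment levels and constraining the baseline means to be equal is an alternative. It is not exactly equivalent when SDs differ over time and only a random intercept is fitted.

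The SAP is written in the past tense, so the interaction results should be shown alongside and the change labelled as such. The cost is a short SAP edit, a re-run of the syntax, and one or two extra parameters. No participant is lost for want of a baseline score. If the slope is near 1, the gain may be negligible.

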Research Proposal

Efficacy of an Attention Guidance VR Intervention for Social Anxiety Disorder

Study Protocol

Date: 06/18/2020

Identifiers: NCT03683823 Unique Protocol ID: 2018-04-0011

Research Proposal

1. Title

Efficacy of an attention guidance VR intervention for social anxiety disorder

2. Principal Investigator

[name], [name], Psychology
[name], [name], Psychology
[name], [name], Psychology

3. Purpose

Social anxiety disorder (SAD) is a prevalent mental health concern with 12% lifetime prevalence^{1,2}. SAD rarely remits without treatment³ and is associated with significant reduction in quality of life^{4,5}, functional impairment⁶, and significant financial burden⁷. Even following treatment, improvements in symptoms are modest, with meta-analyses of empirically supported treatments indicating only moderate effect sizes^{8,9} and remission rates that are only approximately 30-40%¹⁰.

Attentional processes (i.e. how attention is allocated towards salient information) have been implicated in the maintenance of anxiety disorders, including SAD¹¹. Among individuals with SAD, there is evidence of heightened avoidance of faces (i.e. threat of negative social evaluation)^{12,13-16}. This pattern of avoidance may operate as a maintaining risk factor for SAD¹⁷, and thus a potentially important treatment target.

The primary aims of this study are two-fold. First, we propose to conduct a pilot randomized clinical trial to assess the efficacy of an attentional redirection treatment augmentation strategy for enhancing the outcome of exposure therapy for SAD. Second, we propose to conduct mediational analyses to examine whether the experimental intervention exerts its effects by reducing face avoidance.

4. Procedures

See Table 1 (below) for a summary of the visit measures, and Figure 2 (below) for a diagram of the study design. Completion of the entire study is estimated to take approximately 3 ½ hours.

A. Online Prescreen

Participants will complete brief online questionnaires to assess for social anxiety (LSAS and PRPSA). Participants will be invited based on their scores on the LSAS and PRPSA (see Eligibility criteria below).

We will recruit up to 200 participants in order to enroll 80 participants who meet criteria for the study.

VISIT 1

Baseline Assessment (approximately 45 minutes)

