- 1) On the first session, participants will receive a brief standardized psychoeducation module, presented via a 15-minute video recording. This video will also explain the intervention, its rationale, and the procedure.
- 2) Participants will have 5 minutes to plan and outline a speech based on a provided topic; all participants will receive the same topic and will not be allowed to use the outline during the public speaking exposure trials.
- 3) Participants will then give six speeches that are each 3 minutes long on the same topic. All the speeches will be given in the immersive 360°-video environment to a video of audience members. Between speeches participants will have a 1-minute break and will complete the subjective units of distress scale (SUDS) before and after each speech trial.
- 4) Participants will complete steps 2-3 on the second session, with a different speech topic.
- 5) Participants will complete the two intervention sessions within a single week.

Attention Guidance Condition. The experimental attention guidance condition consists of three unique components: (1) the intervention rationale will include information about the importance of visually attending to the faces of the audience; (2) in addition to being provided a speech topic, participants will be given target audience members to focus their gaze on during the speech. They will be told that they should look at and focus on the target audience member for the whole speech; (3) between speeches, the researcher will tell participants the percentage of time they were focused on the target face.

Standard Exposure Condition. Participants in the standard exposure (i.e. control) condition will complete Steps 1-5 above, but will not receive any of the attention guidance components used in the experimental condition.

VISIT 2

Intervention – Session 2 (approximately 45 minutes)

See intervention procedures described above. All procedures are the same as in session 1 with the exclusion of the psychoeducation component.

Post-treatment Assessment (approximately 20 minutes)

Immediately following the second intervention session participants will complete a series of self-report questionnaires and a behavioral approach task.

VISIT 3

1-week Follow-up Assessment (approximately 20 minutes)

One week after the post-treatment assessment participant will return to the lab and complete self-report questionnaires and a behavioral approach task, as in the post-treatment assessment.

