ONLINE FOLLOW-UP

1-month Follow-up Assessment (approximately 10 minutes)

Research Proposal

One month after the 1-week assessment, participants will receive a link to a brief survey containing self-report questionnaires.

[figure not shown]

Figure 2. Presents a diagram illustrating the study overview

Additional Follow-up

In-person Follow-up Assessment (approximately 1 hour)

During the consent process participants will have the option to opt-in to be contacted about an additional follow-up session which will consist of an assessment similar to the baseline assessment conducted during Visit 1 of this study. The primary difference is that the assessment include a speech given to a live audience while using a wearable eye tracking device. Participants will complete a separate ICD for this follow-up appointment and will receive financial compensation.

a. Location

Laboratory for the Study of Anxiety Disorders (rooms: 3.112A, 3.112B, 3.112C, 3.112D, 3.112E, 3.112F, 3.122A, 3.122B, 3.122C, 3.122D, 3.122E, 3.122F), and in the Vision, Cognition, and Action Virtual Reality lab (SEA 4.330).)

b. Resources

[name] departmental account.

c. Study Timeline

Estimated time for study recruitment is two years, plus one year for data analysis.

Table 1. Assessment Schedule

Assessment	Online Prescreen	Baseline Assessment (Visit 1)	Intervention Session 1 (Visit 1)	Intervention Session 2 (Visit 2)	Post-intervention assessment (Visit 2)	1-Week Follow-up (Visit 3)	1-month Follow-up (Online)
DEMO	X	X					
SCID-5		X					
TRT	X	X					X
C-SSRS		X					
BAT		X			X	X	
LSAS	X	X			X	X	X
PRPSA	X	X			X	X	X
SATI		X				X	X
SUDS		X	X	X	X	X	
EYE-TRACK		X	X	X	X	X	
Heart-Rate		X	X	X	X		

Note. DEMO = demographics questionnaire (age, sex, etc.); SCID-5 = Structured Clinical Interview for DSM-5 Disorders; TRT = current treatment assessment; C-SSRS Columbia Suicide Severity Rating Scale; BAT = Behavioral Approach Task to assess peak fear, which will consist of giving a three-minute speech to an audience that is different from the audience during the intervention; LSAS = Liebowitz Social Anxiety Scale; PRPSA = Personal Report of Public Speaking Anxiety; SATI = Speech Anxiety Thoughts Inventory; SUDS = subjective units of distress scale (e.g. peak fear); EYE-TRACK = Eye tracking data. Heart-Rate = Heart rate data.

5. Measures (see table 1 above for time points at which measures will be given)

Screening and other questionnaires or assessments

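### As its text reads, the aim 2 mediation model adjusts for gaze measured after randomisation and names no baseline term, so the indirect effect can be biased

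*SAP*

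**What the plan says.** The SAP's Data Analysis Plan gives the second primary aim as to "test whether changes in gaze behavior following the intervention mediated the effects VRET". Protocol section 3 gives it as to "examine whether the experimental intervention exerts its effects by reducing face avoidance".

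The mediator in the SAP text is a post-treatment level: "the indirect (i.e., mediating) effect of proportion of fixations to uninterested (socially threatening audience members) at the post-treatment assessment". It is placed on "the relationship between intervention group and the post-treatment assessment of PRPSA at the 1-week-followup", which I read as the 1-week score. The same analyses are repeated for the LSAS.

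On covariates the text has one rule: "In all models, we included average proportion of fixations to audience members during intervention sessions as a covariate to control for variation in treatment adherence". It names no baseline score and no baseline gaze measure for aim 2. Later in the same section, as an integrity check, "we tested whether there were group differences for average number of fixations on audience members during the intervention trials".

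The protocol places randomisation after the baseline assessment and before session 1. In the attention guidance arm only, participants are given a target face ("They will be told that they should look at and focus on the target audience member for the whole speech") and feedback between speeches on how long they looked at it. Table 1 marks PRPSA, LSAS and eye tracking ("EYE-TRACK = Eye tracking data") at baseline. The sensitivity analyses in the SAP vary the priors only.

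**The concern.** An indirect effect is the product of two paths: group to gaze (a) and gaze to outcome (b). Randomisation protects a. It does not protect b, because nobody is randomised to a level of post-treatment gaze.

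Two features of the text bear on this. First, the covariate is measured after allocation, in sessions where only one arm is told where to look. If it differs by arm, adjusting for it changes a, the path that randomisation would otherwise protect. Second, participants who avoid faces at baseline may also be more anxious at baseline. If both traits persist, post-treatment gaze and the 1-week score are associated even when gaze has no effect. No chance imbalance between arms is needed for that.

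Aim 2 is one of two primary aims of a pilot meant to show whether a larger trial is worthwhile. A gaze mechanism that is masked, or that partly reflects stable differences between people, would misinform that decision. Changing the priors removes neither problem.

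**Working it through.** **No plan figure to reproduce.** The documents give no path sizes, SDs, gaze-anxiety correlation, stability or achieved N. The simulated sample size of 60 comes without inputs and does not bear on this point. Every input below is assumed. Ordinary least squares stands in for the Bayesian model, in SD units.

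**Order of measurement.** Baseline PRPSA, LSAS and gaze; randomisation; in-session fixations; post-treatment gaze; 1-week outcome. The one named covariate lies between randomisation and the mediator.

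**Assumed inputs.** Baseline gaze and baseline PRPSA correlate r. In-session fixations correlate 0.5 with baseline gaze within arm and differ by d between arms. Post-treatment gaze has a = 0.80 and stability 0.6. PRPSA stability is 0.7. In-session gaze at first has no effect on later gaze (no carry-over).

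**Path a.** Within arm, the slope of post-treatment gaze on in-session fixations is 0.6 x 0.5 = 0.30. The fitted a is therefore 0.80 - 0.30d:

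- d = 0: 0.80
- d = 0.25: 0.725
- d = 0.5: 0.65
- d = 1: 0.50

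With carry-over of 0.3 and stability held at 0.6, the slope is 0.3 + (0.6 - 0.3 x 0.5) x 0.5 = 0.525. The fitted a is then 0.67, 0.54 and 0.28 at d = 0.25, 0.5 and 1.

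**Path b, true value 0.** Given group and in-session fixations, the bias is 0.7 x (0.6r - 0.30 x 0.5r) / (1 - 0.30²) = 0.315r / 0.91 = 0.346r. This is 0 at r = 0, -0.07 at r = -0.2 and -0.14 at r = -0.4. Simulation at N = 40 and 60 agrees. With gaze stability 0.5 to 0.7, PRPSA stability 0.5 to 0.8 and covariate correlation 0.3 to 0.7, the bias is -0.03 to -0.10 (r = -0.2) and -0.06 to -0.21 (r = -0.4).

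Baseline PRPSA alone removes it. If baseline gaze also acts directly on the outcome (-0.1 or -0.2, with r = -0.2), the bias is -0.12 or -0.17 as the text reads, -0.05 or -0.10 with baseline PRPSA, and about 0 with both terms.

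**Indirect effect, true b = -0.2.** The true product is 0.80 x -0.2 = -0.16. At d = 0.5, as the text reads and without carry-over, it is 0.65 x (-0.2 + 0.346r):

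- r = 0: -0.130
- r = -0.2: -0.175
- r = -0.4: -0.220

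With carry-over and r = 0 it is 0.5375 x -0.2 = -0.108. Hence -0.11 to -0.22, on both sides of the truth.

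**A second assumed set.** Group to in-session gaze 1.0, carry-over 0.4, direct group effect on later gaze 0.2, b = -0.3. Baseline gaze acts on both in-session and later gaze with weight 0.4, and in-session gaze has within-arm variance 0.80. True a is 0.2 + 0.4 = 0.60 and the true product is -0.18. The slope is 0.4 + 0.4 x 0.4 / 0.80 = 0.60, so the fitted a is 0.60 - 0.60 = 0 and the mediated effect vanishes. If the whole group effect runs through in-session gaze (carry-over 0.6), the slope is 0.80 and the fitted a is -0.20. With a baseline correlation of -0.3, the fitted b is -0.395 and the product is +0.079.

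**Which adjustment recovers the truth.** Return to the first set with d = 0.5, carry-over 0.3 and a direct in-session effect on outcome of -0.2 (true product -0.16).

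- In-session fixations in both equations, with both baseline terms: 0.65 x -0.2 = -0.13.
- In neither equation, with both baseline terms: b = -0.2 - 0.2 x (0.3 x 0.75) / 0.64 = -0.27, and 0.80 x -0.27 = about -0.22.
- In the outcome equation only, with the baseline outcome: 0.80 x -0.20 = -0.16.

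**Precision.** SE of b at N = 40, r = -0.2:

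| Gaze / PRPSA stability | As read | Plus baseline PRPSA | Plus baseline PRPSA and gaze |
|---|---|---|---|
| 0.6 / 0.7 | 0.174 | 0.127 | 0.153 |
| 0.6 / 0.6 | 0.174 | 0.142 | 0.171 |
| 0.7 / 0.6 | 0.177 | 0.145 | 0.192 |
| 0.7 / 0.5 | 0.178 | 0.157 | 0.208 |
| 0.6 / 0.4 | 0.175 | 0.163 | 0.197 |

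Baseline PRPSA alone narrows the SE in all five cases. Adding baseline gaze as well leaves it wider than as read in three of five.

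**The case against.** The prose may be only a summary. The SAP refers to Figure 3 for the mediation model and to posted syntax, and either could contain baseline terms. That stands, and limits the baseline half to what the text names. It does not touch the covariate rule, which is explicit.

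The covariate has a stated purpose, treatment adherence, and it is not the trained behaviour: it covers audience members generally, while training concerns one target face. The integrity check uses the number of fixations, whereas the covariate is a proportion. Testing for an arm difference is also not evidence of one. All of this stands, and with no arm difference path a is undisturbed. But the targets are themselves audience members, so a difference is plausible, and an adherence rationale does not prevent the distortion.

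The b-path bias may be small. Entry requires PRPSA above 98, LSAS above 30, fear on the speech task and a diagnosis, which can attenuate any gaze-anxiety correlation. At r = -0.2 the bias is about 0.4 of its SE (0.07 / 0.174). The calculation also ignores the informative priors. These points stand as limits on size.

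A reader might infer that the fitted model omitted baseline, that the arms differed on the covariate, or that the aim 2 result is wrong in a known direction. The documents support none of these: the code is unseen, no in-session data are given, and the two biases can oppose each other.

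**Conclusion.** The concern holds for the model as the text describes it. The rule of adjusting every model for in-session fixations puts a post-randomisation variable into the group-to-gaze equation, and distorts that path to the extent that the variable differs by arm. The text also names no baseline term to protect the gaze-to-outcome path. That second bias is zero if baseline gaze and anxiety are uncorrelated and baseline gaze has no direct effect on the outcome.

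Neither size nor net direction follows from the documents. The illustrations run from modest shifts to a vanished or sign-reversed indirect effect, and they show only that the matter is not negligible under plausible inputs. It should be corrected or clarified, with medium confidence, since unseen material may already settle the baseline half.

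**What to change.** 1. Leave in-session fixations out of the group-to-gaze equation. If they are wanted, keep them only in the gaze-to-outcome equation.
2. Add the baseline outcome score (PRPSA or LSAS, as applicable) to both equations, and list each equation's covariates in the SAP text.
3. Add baseline fixations to uninterested audience members as a sensitivity analysis, since the aim concerns change in gaze. This assumes they can be scored from the baseline speech.
4. Report the result beside the model as run, labelled as an added analysis because the SAP describes work already done. If the posted syntax already contains these terms, state that instead.
5. State that unmeasured mediator-outcome confounding remains.

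The cost is a few model runs per outcome on measures already scheduled, plus wording. The added models are post hoc and bring more parameters to a small sample. Baseline gaze may widen the interval for b (for example, SE 0.178 to 0.208), which is why it belongs in a sensitivity analysis. With in-session fixations in the outcome equation only, the group coefficient and the indirect effect no longer sum to the total effect: any direct effect of in-session gaze lies outside both (0.5 x -0.2 = -0.10 in the example above). The report should say so.
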